8. SAFETY REPORTING

Adverse events and device deficiencies, noted by study staff and reported by the subject, and occurring from the time of study device implantation through to study completion should be recorded on the appropriate CRFs and reported as below. Adverse event definitions are as per ISO 14155:2011.

8.1. Definitions for safety reporting

A. Adverse Event (AE)

An AE is any untoward medical occurrence, unintended disease or injury, or untoward clinical signs (including abnormal laboratory findings) in subjects, users or other persons, whether or not related to the study medical device.

This definition includes but is not limited to:

- events related to the study device
- events related to the procedures involved

B. Serious Adverse Event (SAE)

A SAE is an adverse event that:

- resulted in death,
- was life threatening (at the time of the event); or
- resulted in hospitalization (initial or prolonged); or

Smith & Nephew - Advanced Surgical Devices Division

Post-Approval Study of the R3™ Biolox® delta Ceramic Acetabular System – United States	Number: 16-4565-10
	Version 6.0
	Page: 18 of 28

- resulted in a disability or permanent damage (a significant, persistent or permanent change, impairment, damage or disruption in the patient's body function/structure, physical activities and/or quality of life); or
- resulted in a congenital anomaly or birth defect; or
- required medical or surgical intervention to preclude permanent impairment of a body function or prevent permanent damage to a body structure; or
- does not fit the other outcomes above, but may jeopardize the subject and may require medical or surgical intervention (treatment) to prevent one of the other outcomes.

Planned hospitalization for a pre-existing condition, or a procedure required by the protocol, without serious deterioration in health, is not considered a serious adverse event.

C. Adverse Device Effect (ADE)

An ADE is an adverse event related to the use of an investigational medical device [2].

This definition includes:

- adverse events resulting from insufficient or inadequate instructions for use, deployment, implantation, installation, or operation, or any malfunction of the investigational medical device
- any event resulting from use error or from intentional misuse of the investigational medical device.

D. Serious Adverse Device Effect (SADE)

A SADE is an adverse device effect that has resulted in any of the consequences characteristic of a serious adverse event [2].

E. Unanticipated Serious Adverse Device Effect (USADE)

Any serious adverse effect on health or safety or any life-threatening problem or death caused by, or associated with, a device, if that effect, problem, or death was not previously identified in nature, severity, or degree of incidence in the investigational plan or application (including a supplementary plan or application), or any other unanticipated serious problem associated with the device that relates to the rights, safety, or welfare of subjects.

F. Device Deficiency

A device deficiency is an inadequacy of a medical device with respect to its identity, quality, durability, reliability, safety or performance. Device deficiencies include malfunctions, use errors, and inadequate labelling.

For the purpose of this study, device deficiencies should be reported when they concern any component of the study device as well as its packaging and tools that need to be used during implantation according to the Instructions for Use.

G. Revisions

A specially designed Study Implant Disposition (Hip) Form will be used in addition to the Adverse Event Form, to document in detail revisions of any of the components of the study device.

Smith & Nephew - Advanced Surgical Devices Division

Post-Approval Study of the R3™ Biolox® delta Ceramic Acetabular System – United States	Number: 16-4565-10
	Version 6.0
	Page: 19 of 28

8.2. Safety: Investigator's Responsibilities

Investigators shall record adverse events and observed device deficiencies, together with an assessment of seriousness, severity, and device/procedure relatedness, in the subject's source data. Following, Investigators are responsible for documenting AEs and device deficiencies on the appropriate CRF and submitting them to the Sponsor according to the timelines described here below.

At each contact with the subject, the Investigator must seek information on AEs by specific questioning and, as appropriate, by assessment of the subject. AEs must be recorded in standard English medical terminology.

Unresolved AEs should be followed by the Investigator until the events are resolved, the subject is lost to follow-up or through to the end of the study, whichever timing occurs first. Unresolved AEs at the end of the subject's participation will be monitored by the Investigator as part of the site's normal standard of care.

The Investigator will categorize AEs as mild, moderate or severe based on the following definitions:

- Mild: the subject is aware of the sign or symptom, but finds it easily tolerated. The event is of little concern to the subject and/or little clinical significance. The event is not expected to have any effect on the subject's overall health or wellbeing.
- Moderate: the subject has discomfort enough to cause interference with or change in usual activities. The event is of some concern to the subject's health or wellbeing and may require medical intervention and/or close follow-up.
- Severe: the adverse event interferes considerably with the subject's usual activities. The event is of definite concern to the subject and/or poses substantial risk to the subject's health or wellbeing. The event is likely to require medical intervention and/or close follow-up and may be incapacitating or life threatening. Hospitalization and treatment may be required.

The Investigator is responsible for describing the relationship of the AE to the study device/procedure based on the following definitions:

- Unrelated: the event is clearly not related to the study device or procedure
- Possible: the event may or may not be related to the study device or procedure. A relationship cannot be ruled out.
- Definite: the event is clearly related to the study device or procedure.

8.3. Timelines for Submission of Safety Information:

The timelines begin when the Investigator becomes aware of the event.

The Investigator will report to the Sponsor:

- As soon as possible, but no greater than **24 hours upon becoming aware of the event, SAEs, SADEs, U(S)ADEs and device deficiencies that could have led to a SADE:**
 - if suitable action had not been taken

Smith & Nephew - Advanced Surgical Devices Division

Post-Approval Study of the R3™ Biolox® delta Ceramic Acetabular System – United States	Number: 16-4565-10
	Version 6.0
	Page: 20 of 28

- if intervention had not been made, or
- if circumstances had been less fortunate
- **Rewards, within 24 hours upon becoming aware of the event.** Sponsor will provide an explant retrieval kit on becoming aware of a revision and ask the Investigator to return any revised components for retrieval analysis.

Investigators may also be asked to supply the Sponsor, upon Sponsor's request, with any additional information related to the safety reporting of a particular event. Investigators will be responsible for complying with the adverse event reporting requirements of the IRB/EC at the study site.

8.4. Safety reporting: Sponsor's Responsibilities

Sponsor will provide progress reports on safety events to the Investigator to report to the IRB/EC as required. The Sponsor will also, in case of SADEs and device deficiencies that could have led to SADEs, determine whether the risk analysis needs to be updated and assess whether corrective or preventive action is required.

9. STATISTICAL PROCEDURES

9.1. General considerations

Categorical variables will be summarized with the number and percent of subjects in each group. Continuous variables will be summarized with the mean, standard deviation, median, minimum, and maximum values. 95% confidence intervals will be calculated for the primary and secondary endpoints. The primary endpoint will be analyzed using the exact binomial test method.

A complete Statistical Analysis Plan (SAP) is included in Appendix IV.

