9.2. Sample size calculation

The primary objective of this study is to confirm that the safety and effectiveness of the R3 Biolox delta Ceramic Acetabular System in the US population is consistent with the effectiveness and safety profile shown in the European study (PMA cohort). The primary endpoint is overall study success at 3 years postoperative. Secondary endpoints include clinical assessments of pain and function, radiographic findings and survivorship.

Overall success (as defined in the section entitled "Data Collection: Study Endpoints") in the PMA Cohort was found to be 86.4% at 3 years post-surgery for the Biolox delta ceramic-on-ceramic (DOD) treatment group. It is expected that the overall success for the DOD US Cohort is similar to the overall success to the DOD PMA Cohort (European data).

Statistical Hypotheses:

$$H_0: \pi_{DOD} - 0.864 \leq \delta$$

$$H_a: \pi_{DOD} - 0.864 > \delta$$

Smith & Nephew - Advanced Surgical Devices Division

Post-Approval Study of the R3™ Biolox® delta Ceramic Acetabular System – United States	Number: 16-4565-10
	Version 6.0
	Page: 21 of 28

Where,

π_{DOD} = Overall Success of DOD US

1-sided alpha error = 5%

Power of the test = 80%

$\delta = -0.08$

The minimum sample size required for hypothesis testing: 146 DOD US subjects. The total sample size after adjustment for lost-to-follow-up (20%) is 183 DOD subjects. Sample size was calculated assuming use of an Exact Binomial test [1].

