5.2 Secondary Endpoint(s)

Secondary endpoints include clinical assessments of pain and function using the modified Harris Hip Score, radiographic findings, and implant survivorship.

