7.2.2 Enrolled set

Every subject that receives the study device will be considered enrolled in the study and included in the Enrolled set. If a subject has provided consent and completed screening, and for any reason does not receive the study device, the subject will not be considered enrolled in the study.

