7.11 Analysis of Secondary Endpoint(s)

Secondary endpoints include clinical assessments of pain and function using the modified Harris Hip Score, radiographic findings, and implant survivorship. These assessments will be summarized using descriptive statistics at postoperative visits. No analyses are planned.

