7.13 Analysis of Safety Endpoint(s)

The number of AEs, SAEs, USADEs, Reoperation and Revisions, and the number and the percentage of patients experiencing AEs, SAEs, USADEs will be presented for the enrolled set.

The number of AEs and the number and the percentage of patients with at least one AE will be presented for AEs and SAEs.

The number and the percentage of patients with at least one AE will be presented by severity, seriousness, device relatedness and procedure relatedness.

Adverse event definitions are shown below and are as per the study protocol.

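### Adverse-event results are planned as crude percentages of the Enrolled set, with no confidence interval and no allowance for subjects who leave early

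*Protocol*

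**What the plan says.** **Statistic and denominator.** Protocol 9.1 gives the general rule, "Categorical variables will be summarized with the number and percent of subjects in each group", but sets no safety denominator. SAP 7.13 does: "the number and the percentage of patients experiencing AEs, SAEs, USADEs will be presented for the enrolled set". SAP 7.2.2 defines that set: "Every subject that receives the study device will be considered enrolled in the study and included in the Enrolled set". In the same paragraph of SAP 7.13, reoperations and revisions are given as numbers, without a patient percentage.

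**Intervals.** Protocol 9.1 and SAP 7.1 both state: "95% confidence intervals will be calculated for the primary and secondary endpoints". SAP 5.2 says which endpoints are secondary: "Secondary endpoints include clinical assessments of pain and function using the modified Harris Hip Score, radiographic findings, and implant survivorship". Adverse events and device deficiencies sit apart, as safety endpoints in SAP 5.4.

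**Follow-up.** Protocol 9.2 and SAP 6.1 allow for incomplete follow-up: "The total sample size after adjustment for lost-to-follow-up (20%) is 183 DOD subjects". Neither document specifies time at risk, person-time or a time-to-event summary for adverse events. The accountability table in SAP 7.6 gives follow-up rates by visit but is not tied to the AE denominators.

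**The concern.** The objective (Protocol 2, SAP 4) is to confirm that safety, as well as effectiveness, in US patients is in line with the European cohort, which was followed to 3 years. Two things are missing for the safety half.

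First, without an interval a reader cannot tell an AE percentage that agrees with the European experience from one that is merely imprecise. This matters most for rare events. Protocol 10.4 names femoral head breakage and liner fracture as risks of ceramic bearings. If none occurred, the report would show zero without saying how large a risk the study can exclude.

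Second, a subject who withdraws or cannot be contacted after a few months, with no event recorded, stays in the denominator as a patient without an event. Follow-up lasts 3 years, so readers are likely to take the percentage as a 3-year risk. Read that way it is too low, and it falls further as loss rises.

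**Working it through.** **1. The plan's own figures.** Inputs from Protocol 9.2: reference rate 86.4%, margin 8 points (null rate 78.4%), one-sided alpha 5%, power 80%. With the exact binomial test, the smallest n reaching 80% power is 146: success is declared at 123 or more of 146, with exact alpha 0.0492 and power 0.8125. This agrees with the plan: "The minimum sample size required for hypothesis testing: 146 DOD US subjects". Allowing for 20% loss, 146 / 0.80 = 182.5, rounded up to 183. The allowance is therefore 183 − 146 = 37 subjects.

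**2. What a zero count can exclude.** For 0 events in n, the exact (Clopper-Pearson) two-sided 95% upper limit is 1 − 0.025^(1/n).

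- n = 183: 1 − 0.025^(1/183) = 2.0%
- n = 146: 1 − 0.025^(1/146) = 2.5%

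Exact 95% intervals for some other counts in 183:

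| Events | Percentage | Exact 95% interval |
|---|---|---|
| 1 | 0.5% | 0.01% to 3.0% |
| 5 | 2.7% | 0.9% to 6.3% |
| 18 | 9.8% | 5.9% to 15.1% |

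None of this depends on an assumption about loss.

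**3. How far the crude percentage falls below 3-year risk.** The documents give neither AE rates nor their timing, so both are assumed here. Let F be the true 3-year risk. Suppose 20% of subjects cease to yield AE information, independently of their risk, at a time C. Then

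expected crude proportion = 0.8F + 0.2 × (mean risk accrued by time C).

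If C is uniform over 3 years, a share e of events is perioperative and the rest are spread evenly, the mean risk accrued by C is eF + 0.5(1 − e)F. The crude proportion is then F × (0.9 + 0.1e).

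| Assumption | Factor | A true 10% appears as | Relative shortfall |
|---|---|---|---|
| Events evenly spread (e = 0) | 0.90 | 9.0% | 10% |
| Half perioperative (e = 0.5) | 0.95 | 9.5% | 5% |
| 80% perioperative (e = 0.8) | 0.98 | 9.8% | 2% |
| Bound: all loss right after surgery, no perioperative events | 0.80 | 8.0% | 20% |

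The last row is the limit under independent loss, because the second term cannot be negative. If subjects with complications are more likely to leave unreported, the shortfall could exceed it.

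**4. Relative importance.** At a true 10% the plausible shortfall is 0.2 to 1.0 points. The standard error of a proportion of 10% in 183 is √(0.1 × 0.9 / 183) = 2.2 points. Imprecision is larger than bias, and at present neither is shown.

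**The case against.** Much of the case on the other side stands.

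- A reader might infer that subjects who die or are revised are carried as event-free. The documents do not support that. An event resulting in death is an SAE by definition (Protocol 8.1 B, SAP 7.13.2), and a revision is documented on an Adverse Event Form as well as its own form (Protocol 8.1 G). The concern is limited to subjects who withdraw or become unreachable.
- A reader might infer that no safety result has an interval. That is too broad. Revision is a component of the primary endpoint, and implant survivorship is a secondary endpoint, so the general sentence gives both a 95% interval. One qualification applies to survivorship: SAP 7.11 names no estimator and says "These assessments will be summarized using descriptive statistics at postoperative visits. No analyses are planned".
- A reader might infer that the plan expects 20% of AE information to be lost. The 20% is a sample-size allowance for a primary endpoint that needs the mHHS and radiographs. Subjects who miss visits may be telephoned about adverse events, and SAP 7.3 uses those data where it can. Recovery is only partial, however: Protocol 6.5 asks about any adverse event, while SAP 3.2.4 asks only about those related to the hip device.
- SAP 7.13 does not call its percentages 3-year rates. As observed proportions they are correct. They understate only if read as 3-year risks.
- Since the count and denominator are reported, a reader could work out the zero-count limit. That is true, but the report should supply it when safety is part of the objective.
- The documents do not say how adverse events were summarised in the European cohort. If they were crude percentages, a time-to-event estimate alone would not match them. This is a reason to keep the crude percentages, not a reason to leave out intervals.

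**Conclusion.** The point holds for AEs, SAEs, USADEs and reoperations. Their planned summaries have no interval and make no allowance for early exit. The firm part is the missing interval, which rests on no assumption: zero events would be shown without an upper limit of 2.0% (0 of 183) or 2.5% (0 of 146).

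The understatement of 3-year risk is real in direction but modest: about 2 to 10% relative if the whole 20% allowance were uniform, independent loss of AE information, and at most 20% relative under any independent loss. Those sizes rest on assumed event rates and timing and on treating a planning allowance as actual AE loss. The stronger conclusion, that reported safety rates will be materially wrong in the device's favour, is not supported. The sample size and the primary test are unaffected.

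**What to change.** 1. In SAP 7.13, add exact (Clopper-Pearson) 95% intervals to the patient-level AE, SAE and USADE percentages, zero counts included. Add a patient-level percentage with its interval for reoperation. State whether a revision counts as a reoperation, since the section lists the two side by side.
2. In Protocol 9.1 and SAP 7.1, extend the interval sentence to safety endpoints.
3. Keep the crude percentages for comparison with the PMA cohort. Beside them, as supporting information, show the 3-year cumulative incidence with 95% interval and numbers at risk for first SAE, first device-related AE and first reoperation. Censor at last contact. Treat death as a competing event for device-related AE and reoperation; for SAE, death is itself an event.
4. Add a date rule for these estimates. SAP 7.3 sets partial dates to the first of the month or to January 1, which can fall before the operation, so an imputed onset should not be allowed to precede surgery. AEs with no date at all, which SAP 7.3 keeps, also need a stated convention.

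**Cost.** SAP and Protocol wording, a few extra table columns, the date rule, and slightly higher reported rates. No new subjects, visits or data collection are needed. The cumulative incidence still assumes that loss is unrelated to complications, and the report should say so.

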9.2. Sample size calculation

The primary objective of this study is to confirm that the safety and effectiveness of the R3 Biolox delta Ceramic Acetabular System in the US population is consistent with the effectiveness and safety profile shown in the European study (PMA cohort). The primary endpoint is overall study success at 3 years postoperative. Secondary endpoints include clinical assessments of pain and function, radiographic findings and survivorship.

Overall success (as defined in the section entitled "Data Collection: Study Endpoints") in the PMA Cohort was found to be 86.4% at 3 years post-surgery for the Biolox delta ceramic-on-ceramic (DOD) treatment group. It is expected that the overall success for the DOD US Cohort is similar to the overall success to the DOD PMA Cohort (European data).

Statistical Hypotheses:

$$H_0: \pi_{DOD} - 0.864 \leq \delta$$

$$H_a: \pi_{DOD} - 0.864 > \delta$$

Smith & Nephew - Advanced Surgical Devices Division

Post-Approval Study of the R3™ Biolox® delta Ceramic Acetabular System – United States	Number: 16-4565-10
	Version 6.0
	Page: 21 of 28

Where,

π_{DOD} = Overall Success of DOD US

1-sided alpha error = 5%

Power of the test = 80%

$\delta = -0.08$

The minimum sample size required for hypothesis testing: 146 DOD US subjects. The total sample size after adjustment for lost-to-follow-up (20%) is 183 DOD subjects. Sample size was calculated assuming use of an Exact Binomial test [1].

10. ETHICAL CONSIDERATIONS

10.1. Ethical Approval

In accordance with the Declaration of Helsinki and local regulations of the participating countries, sites must gain written IRB/EC approval prior to enrolling research participants in the study.

10.2. Protocol Amendments

Neither the Investigator nor the Sponsor will modify this protocol without mutual agreement. After agreement to initiate the modification - in the form of a protocol amendment - the Investigator agrees not to implement this modification until instructed to do so by the Sponsor. It will be necessary to obtain US FDA and IRB/EC approval prior to implementation of any change in the protocol that may affect the scientific soundness or the rights, safety, or welfare of the subjects involved. Notification shall be submitted to the Central IRB and IRB/EC of the study site by the Investigator for active sites.

10.3. Informed Consent

All study subjects must sign an IRB/EC approved ICF according to ISO14155:2011 guidelines, GCP guidelines and all applicable national regulations. Potential subjects must be informed as to the purpose of the study and the potential risks and benefits known or that can be reasonably predicted or expected as described in the written consent form. The subject shall have sufficient opportunity to consider participation in the study; a subject cannot be led to believe that they are waiving their rights as a subject or the liability of the Sponsor or Investigator. Subjects are then invited to sign and date the consent form, indicating their consent for enrollment. The Investigator will retain the original copy of the signed consent form in the study files. A duplicate copy shall be provided to the subject.

10.4. Risk – Benefit Analysis

A. Study Related Risks

The study involves the standard assessment of a primary total hip arthroplasty (THA) procedure. The R3 delta Ceramic Acetabular System has been approved for use by the FDA and will be used according to its labeling.

Potential Complications Associated with Any Total Hip Arthroplasty surgery:

Smith & Nephew - Advanced Surgical Devices Division

Post-Approval Study of the R3™ Biolox® delta Ceramic Acetabular System – United States	Number: 16-4565-10
	Version 6.0
	Page: 22 of 28

- Excessive wear of the implant components secondary to impingement of components or damage of articular surfaces
- Fracture, migration, loosening, subluxation, or dislocation of the prosthesis or any of its components; any of which may require a second surgical intervention or revision;
- Increased hip pain and/or reduced hip function
- Bone fractures
- Osteolysis and/or other peri-prosthetic bone loss
- Metal sensitivity reactions or other allergic/histological reactions to implant material
- Vascular damage resulting in significant blood loss, or
- Neurologic injury resulting in transient or permanent functional and/or sensory deficits
- Leg length change/discrepancy
- Deep venous thrombosis
- Pulmonary or vascular embolism
- Superficial or deep infection, delayed wound healing
- Periarticular calcification
- Myocardial infarction
- Gastrointestinal complications
- Genitourinary complications
- Decreased range of motion
- Aggravation of other joint or back conditions (due to positioning during surgery, postoperative leg length discrepancy, muscular deficiencies, etc.)
- Death

Potential Complications Associated with Ceramic on Ceramic Hip Systems:

- Due to the materials of the device, these may include, but are not limited to, femoral head breakage, acetabular insert (liner) fracture, and device related noise such as squeaking. Other adverse events, common to other hip systems may also occur but at different frequencies.

Possible risks that may occur as a result of study procedures are:

- This study involves the use of x-ray evaluation. X-ray exposure is cumulative over a lifetime and total exposure should be kept to a minimum. However, if the x-ray exposure when participating in the study is equivalent to the exposure the subject would receive if they chose not to participate in the study, there is no additional risk associated with this study.
- As a result of participating in the study there could be a risk of loss of protected subject information confidentiality. All applicable confidentiality standards and data protection and privacy laws will be followed by the Sponsor to ensure that data collected is handled in confidence. Data will be coded and handled only by appropriately qualified and authorized personnel.

Risks related to the general surgical procedures are not considered here because these could be present regardless of participation into the study.

B. Study Related Benefits

Smith & Nephew - Advanced Surgical Devices Division

Post-Approval Study of the R3™ Biolox® delta Ceramic Acetabular System – United States	Number: 16-4565-10
	Version 6.0
	Page: 23 of 28

Because the surgery and all the follow-up visits are the same as when the subject would not participate in this study, there are no additional medical benefits associated by participating in this study. The information gained from this study may help improve the treatment of people that need to undergo total hip arthroplasty.

